### 14.5 Vital Signs Criteria for Markedly Abnormal Values

Parameter (unit)	Age (years old)	Markedly Low	Markedly High
SBP (supine, standing) (mmHg)	6-12	Value $\leq$ 70 and $\geq$ 20 decrease from baseline	Value $\geq$ 120 and $\geq$ 20 increase from baseline
	13-18	Value $\leq$ 90 and $\geq$ 20 decrease from baseline	Value $\geq$ 135 and $\geq$ 20 increase from baseline
DBP (supine, standing) (mmHg)	6-12	Value $\leq$ 40 and $\geq$ 15 decrease from baseline	Value $\geq$ 80 and $\geq$ 15 increase from baseline
	13-18	Value $\leq$ 50 and $\geq$ 15 decrease from baseline	Value $\geq$ 90 and $\geq$ 15 increase from baseline
Pulse rate (supine, standing) (bpm)	6-10	Value $\leq$ 60 and $\geq$ 15 decrease from baseline	Value $\geq$ 135 and $\geq$ 15 increase from baseline
	11-18	Value $\leq$ 50 and $\geq$ 15 decrease from baseline	Value $\geq$ 120 and $\geq$ 15 increase from baseline
SBP orthostatic criteria (mmHg)	~	$\geq$ 20 decrease from supine to standing position	NA
DBP orthostatic criteria (mmHg)	~	$\geq$ 10 decrease from supine to standing position	NA
Pulse rate orthostatic criteria (bpm)	~	NA	$\geq$ 20 increase from supine to standing position
Temperature ( $^{\circ}$ C)	~	NA	Value $\geq$ 38.3 $^{\circ}$ C and $\geq$ 0.8 $^{\circ}$ C increase from baseline

Note: ~ means that the abnormal range is applicable for all subjects within age group: 6 to 17 years old.

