One study was completed that evaluated the safety, tolerability, pharmacokinetic, and pharmacodynamic properties of dasotraline in pediatric (6 – 12 years) and adolescent (13 - 17 years) subjects with ADHD. In this multicenter, open-label study 105 subjects were assigned to single oral doses of dasotraline 1 - 16 mg in a dose-escalating manner. Dasotraline was characterized by slow absorption (median t_{max} was 9.6 to 12 hours) and elimination (median $t_{1/2}$ was 56 to 84 hours) in both pediatric and adolescent subjects. The change in C_{max} with dose was slightly greater than dose proportional. Increase in overall exposure (AUC) with dose was greater than dose proportional. Apparent oral clearance was highest in the lowest dose group relative to the higher dose groups. No deaths, serious adverse events (SAE), or discontinuations because of an adverse event (AE) were reported in this study. The most frequently reported AE by investigators were tachycardia (25 subjects; 23.8%) and electrocardiogram QT prolonged (5 subjects; 4.8%), nearly all of which were considered related to study drug and mild in severity. Tachycardia AEs were reported in both age groups and in every dose cohort. Most events of tachycardia were reported on the day of study drug administration. No subjects experienced QT prolongations > 500 msec. Based on the centrally read electrocardiogram (ECGs) in the study, no clinically significant trends were identified within the ECG results. Blood pressure increased, blood pressure systolic increased, blood pressure orthostatic abnormal, and orthostatic hypotension AEs were reported in 1 subject each. Overall, after dosing, 90 subjects (85.7%) met predefined criteria for orthostatic tachycardia and 40 (38.1%) met predefined criteria for orthostatic hypotension.

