### **8.6 Clinical Laboratory Evaluations**

The following laboratory tests will be performed at Screening (Visit 1) and EOS (Visit 6):

- Clinical Chemistry: Alanine aminotransferase (ALT), Alkaline Phosphatase (ALP), Aspartate aminotransferase (AST), Bicarbonate (HCO3), Bilirubin (Total, Direct, Indirect), Blood Urea Nitrogen (BUN), Calcium (Ca), Chloride (Cl), Creatinine, Glucose, Magnesium (Mg), Phosphorus (P), Potassium (K), Protein (Total), Sodium (Na), Uric Acid, Albumin
- Hematology: Hemoglobin, Hematocrit, Platelet Count, RBC Count, WBC - Total Count, WBC Differential, (Basophils, Eosinophils, Lymphocytes, Monocytes, Neutrophils)
- Urinalysis: Blood, Glucose, Ketones, Leukocyte esterase, Microscopic examination, Nitrites, pH, Protein

Summary statistics for these laboratory panels (clinical chemistry, hematology and urinalysis) will be provided by treatment group and visit. Laboratory data will also be summarized in shift tables presenting summary statistics of raw data and change from baseline values (means, standard deviations, medians, ranges). All clinical laboratory assessments will be listed for each panel.

In addition, the incidence of markedly abnormal post-baseline laboratory values (MAPLV) will be presented to examine the frequency and percentage of subjects that have values that are potentially clinically significant (PCS). These abnormal values will also be flagged in the laboratory listings. These criteria are outlined in Appendix 14.4.

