## **8.8 Vital Signs**

Vital signs, including respiratory rate; body temperature; supine, standing, and orthostatic blood pressure; supine, standing, and orthostatic heart rate; BMI; and body weight, will be measured at all scheduled in-person study visits (Screening [Visit 1 and Visit 2], Visit 4, Visit 5, and EOS [Visit 6]).

Supine systolic blood pressure, standing systolic blood pressure, orthostatic systolic blood pressure, supine diastolic blood pressure, standing diastolic blood pressure, orthostatic diastolic blood pressure, supine heart rate, standing heart rate, orthostatic heart rate, respiratory rate, body temperature, body weight, and BMI will be summarized descriptively for each visit by treatment group for the absolute value and change from baseline values using descriptive statistics.

In addition, the incidence of sponsor-defined markedly abnormal post-baseline vital sign values will be presented to examine the frequency and percentage of subjects that meet the PCS criteria outlined in Appendix 14.5. Vital signs will also be presented in a listing by subject and visit. The listing will include a flag for abnormal values.

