## **8.9 Electrocardiography (ECG)**

A 12-lead ECG will be recorded at Screening (Visit 1) and the EOS visit (Visit 6). All ECGs will be obtained in the supine position, after the subject has been resting supine for at least 5 minutes. The ECG parameters collected will include heart rate, PR interval, RR interval, QT interval, QTc with Bazett correction (QTcB) and QTc with Fridericia correction (QTcF) intervals, QRS duration, and interpretation, including any noted abnormalities. The ECGs will be reviewed and interpreted by the investigator. All data will be assessed for clinical significance.

ECG measurements, overall interpretation and clinical significance will be summarized descriptively for baseline, each post-dose evaluation, and change from baseline to each post-dose evaluation by treatment group. QT interval, QTcB, and QTcF will also be summarized by < 460 msec, >= 460 msec, < 500 msec, and >= 500 msec, as well as change from baseline < 30 msec, >= 30 msec, < 60 msec, and >= 60 msec, by visit, treatment and age group (6-9 years, 10-13 years (age range up to 13 to account for any subjects who were 12 years at screening but 13 years at time of ECG measurement)).

In addition, the incidence of sponsor-defined markedly abnormal post-baseline ECG values will be presented to examine the frequency and percentage of subjects that meet the PCS criteria outlined in Appendix 14.6. ECG results will also be presented in a listing by subject and visit. The listing will include a flag for abnormal values.

Shifts from baseline to EOS visit ECG results will be presented by treatment group for the overall interpretation (e.g., normal to abnormal, or abnormal to normal).

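### The orthostatic criteria in SAP Appendix 14.5 have no baseline condition, so the planned post-baseline count mixes children who already met them before dosing with new cases

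*SAP*

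**What the plan says.** SAP 8.8 states that "the incidence of sponsor-defined markedly abnormal post-baseline vital sign values will be presented to examine the frequency and percentage of subjects" meeting the criteria in Appendix 14.5.

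Within Appendix 14.5 the criteria take two forms:

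- Supine and standing systolic pressure, diastolic pressure and pulse, and temperature, need both an absolute limit and a change from baseline. The high systolic row for ages 6 to 12, for example, adds a "20 increase from baseline" to its limit.
- The three orthostatic rows need only a difference within one visit: for systolic pressure a "20 decrease from supine to standing position", for diastolic pressure a "10 decrease from supine to standing position", and for pulse a "20 increase from supine to standing position", each as a minimum.

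The same structure without a baseline term appears in two other appendices. SAP 8.9 says that "the incidence of sponsor-defined markedly abnormal post-baseline ECG values will be presented", using the absolute heart rate, PR and QRS limits of Appendix 14.6. SAP 8.6 says that "the incidence of markedly abnormal post-baseline laboratory values (MAPLV) will be presented", using the absolute limits or multiples of the normal range in Appendix 14.4.

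SAP 7.1.3 defines baseline for visit-based safety outcomes as the last value before the first dose. None of these three counts refers to it.

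**The concern.** The term post-baseline says when a value was taken, not whether the finding is new. A child who meets an orthostatic criterion on Day 1 before dosing and again on Day 15 enters the count exactly as a child who first meets it on Day 15. The table is labelled incidence, but it holds new cases plus persisting ones.

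This differs from the SAP's own practice. Most rows of Appendix 14.5 use a baseline term, and SAP 8.4 counts an adverse event as treatment-emergent only if it starts, or a prior condition worsens, after dosing begins.

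The orthostatic rows matter most. Protocol 4.3 reports from an earlier open-label single-dose study that "90 subjects (85.7%) met predefined criteria for orthostatic tachycardia and 40 (38.1%) met predefined criteria for orthostatic hypotension" after dosing. With no comparator and no baseline rate given, those figures cannot separate drug from background. The present trial has a placebo arm and pre-dose values, so it can. A count that merges old and new findings uses only part of that advantage, with about 50 children per arm.

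**Working it through.** **Documented figures.** The earlier study had 105 subjects. 90/105 = 85.7% and 40/105 = 38.1%, so both reproduce. They are post-dose rates and do not enter the calculation below.

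**Inputs.**

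- Arm size: 50 (SAP 2.4).
- Baseline prevalence p0, persistence q among children positive at baseline, and new-onset rates among children negative at baseline: not in the documents. All values below are assumptions.

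**Formula.** Rate counted as planned in one arm = p0 × q + (1 − p0) × (new-onset rate). If q is the same in both arms, the first term cancels in the difference:

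observed risk difference = (1 − p0) × (difference in new-onset rates).

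**Risk difference, for a 10-point difference in new cases:**

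| Assumed p0 | Positive at baseline, of 50 | Negative at baseline | Extra new cases on drug | Difference as counted |
|---|---|---|---|---|
| 20% | 10 | 40 | 4 | 4/50 = 8 points |
| 40% | 20 | 30 | 3 | 3/50 = 6 points |
| 60% | 30 | 20 | 2 | 2/50 = 4 points |

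**Risk ratio, for assumed new onset of 10% on placebo and 30% on drug (true ratio 3.00), q = 0.7:**

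- p0 = 0.05: placebo 0.035 + 0.095 = 13.0%; drug 0.035 + 0.285 = 32.0%; ratio 2.46.
- p0 = 0.30: placebo 0.21 + 0.07 = 28.0%; drug 0.21 + 0.21 = 42.0%; ratio 1.50.
- p0 = 0.50: placebo 0.35 + 0.05 = 40.0%; drug 0.35 + 0.15 = 50.0%; ratio 1.25.

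At p0 = 0.30, moving q from 0.5 to 0.9 moves the ratio from 1.64 to 1.41.

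**If persistence differs between arms.** Take p0 = 0.30, with q = 0.6 on placebo and 0.8 on drug. Placebo: 0.18 + 0.07 = 25%. Drug: 0.24 + 0.21 = 45%. The risk difference is 20 points, the same as among children negative at baseline. The ratio is 1.80, still below 3.00. With q = 0.9 on drug, the difference is 0.27 + 0.21 − 0.25 = 23 points. So shrinkage of the risk difference depends on the equal-persistence assumption.

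**Whether another display separates old from new.**

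- SAP 8.8 plans orthostatic pressures and heart rate by visit, as absolute values and as change from baseline, and a by-subject listing with abnormal values flagged. Mean changes do not show how many children newly cross a threshold; the listing does, but only by hand.
- SAP 8.6 plans laboratory shift tables. SAP 8.9 plans a shift table for overall ECG interpretation and categories of QT and QTc change. Neither covers the orthostatic criteria.

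**Whether the data exist.** Protocol 11.4.3 has blood pressure and pulse taken supine and then standing. The schedules place vital signs at Visits 1, 2, 4, 5 and 6. Visit 4 precedes the first evening dose and follows the stimulant washout.

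**The case against.** The strongest reply is that little is lost. Both arms are randomised, so placebo supplies the background rate. An orthostatic criterion is already a within-child change, from lying to standing. No drug-related case drops out of the table: at an assumed p0 of 60%, the same 2 extra children appear whether the denominator is 20 or 50. The tables are descriptive, with no test or decision rule attached, and change-from-baseline summaries and flagged listings sit beside them. All of this stands, and it limits the point to clarity of presentation. It does not answer the point itself: the planned table cannot tell a reader how many of the counted children met the criterion before dosing.

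A reader might infer more than the documents support, in four ways:

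- **That the 85.7% shows a high background rate.** It is a post-dose, uncontrolled figure from subjects aged 6 to 17 given 1 to 16 mg, and its criteria are not shown to match Appendix 14.5. The protocol's remark about every dose cohort concerns reported tachycardia adverse events, not this figure.
- **That a cardiovascular effect would be hidden.** The other displays in SAP 8.8 and 8.9 tell against that, and the risk difference need not shrink.
- **That laboratory and ECG counts are affected to the same degree.** Entry requires laboratory deviations to be judged not clinically relevant (protocol 8.1, criterion 12) and excludes clinically significant abnormal ECGs (8.2, criterion 7). Many laboratory limits are also extreme, and laboratory shift tables are planned. The effect there is probably small.
- **That the planned count should be replaced.** That would drop children who are abnormal at baseline and then worsen.

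**Conclusion.** The point holds for the three orthostatic rows. The criteria carry no baseline term, SAP 8.8 adds none, and no shift table covers them, so new and pre-existing findings are reported together as incidence.

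The size cannot be taken from the documents. Under equal persistence the risk difference is scaled by (1 − p0), giving 8, 6 or 4 points in place of 10 at assumed prevalences of 20%, 40% and 60%. In every case worked here the risk ratio is pulled towards 1. If p0 is near zero, the effect is negligible. The primary analysis and the sample size are not touched. This is an inexpensive improvement to a safety table.

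**What to change.** In SAP 8.8, for the three orthostatic criteria, keep the planned count and add beside it, by treatment group:

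1. the number of children meeting the criterion at baseline, by the SAP 7.1.3 definition (the scheduled value is Visit 4, after washout);
2. the number and percentage newly meeting it after baseline, among children who did not meet it at baseline and have at least one post-baseline value.

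The same columns may be added to the laboratory and ECG tables in SAP 8.6 and 8.9. If so, state that the scheduled baseline there is Visit 1, when a child may still be taking a stimulant.

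The cost is SAP wording, one derived flag and extra table columns; no new measurement is needed. The new-onset percentage rests on fewer children: with 50 per arm and an assumed p0 of 40% or 60%, on 30 or 20. Showing the planned count alongside keeps children who were abnormal at baseline in view.

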## 14.6 12-Lead ECG Criteria for Markedly Abnormal Values

ECG parameter (unit)	Age (years old)	Abnormally Low	Abnormally High
HR (bpm)	6 to <8	< 65	> 115
	8 to <12	< 55	> 110
	12 to <16	< 50	> 105
	≥16	< 50	> 100
PR interval (msec)	6 to <8	--	> 160
	8 to <12	--	> 175
	12 to <16	--	> 180
	≥16	--	> 200
QRS interval (msec)	6 to <8	--	> 100
	8 to <12	--	> 105
	12 to <16	--	> 110
	≥16	--	> 120

## 14.7 Preferred Term for Adverse Events of Special Concern

1. Suicidal ideations, suicidal behavior, suicide attempts, and related events.

SMQ 2000037: Suicide/self-injury	
PT	Code
Columbia suicide severity rating scale abnormal	10075616
Completed suicide	10010144
Depression suicidal	10012397
Intentional overdose	10022523
Intentional self-injury	10022524
Poisoning deliberate	10036000
Self injurious behaviour	10063495
Self-injurious ideation	10051154
Suicidal behaviour	10065604
Suicidal ideation	10042458
Suicide attempt	10042464
Suicide threat	10077417

2. Spontaneous abortion / miscarriage

SMQ 20000192: Termination of pregnancy and risk of abortion	
PT	Code
Abnormal product of conception	10060927
Aborted pregnancy	10000209
Abortion	10000210
Abortion complete	10061614
Abortion complete complicated	10000212
Abortion complicated	10061615
Abortion early	10052846
Abortion incomplete	10000217
Abortion incomplete complicated	10000218
Abortion induced	10000220
Abortion induced complete	10060928
Abortion induced complete complicated	10000221
Abortion induced complicated	10000223
Abortion induced incomplete	10053984
Abortion induced incomplete complicated	10000225
Abortion infected	10000228
Abortion late	10052847
Abortion missed	10000230
Abortion of ectopic pregnancy	10066266
Abortion spontaneous	10000234
Abortion spontaneous complete	10061616
Abortion spontaneous complete complicated	10000236
Abortion spontaneous complicated	10000238
Abortion spontaneous incomplete	10061617

Abortion spontaneous incomplete complicated	10000239
Abortion threatened	10000242
Biochemical pregnancy	10063639
Blighted ovum	10005160
Ectopic pregnancy termination	10014168
Evacuation of retained products of conception	10015550
Foetal death	10055690
Foeticide	10075033
Habitual abortion	10062935
Imminent abortion	10051459
Induced abortion failed	10053191
Induced abortion haemorrhage	10052844
Induced abortion infection	10052845
Molar abortion	10065942
Mycoplasmal postabortal fever	10028479
Post abortion complication	10036244
Post abortion haemorrhage	10036246
Post abortion infection	10061467
Premature baby death	10076700
Prophylaxis of abortion	10065000
Retained products of conception	10038773
Selective abortion	10067499
Stillbirth	10042062
Twin reversed arterial perfusion sequence malformation	10073455
Vanishing twin syndrome	10071398

### 3. Neuropsychiatric events

SMQ 20000117: Psychosis and psychotic disorders	
PT	Code
Abnormal behaviour	10061422
Abulia	10050013
Acute psychosis	10001022
Affect lability	10054196
Affective ambivalence	10077173
Affective disorder	10001443
Alcohol withdrawal syndrome	10053164
Alcoholic psychosis	10001632
Alice in wonderland syndrome	10001666
Anosognosia	10068346
Apathy	10002942
Asocial behaviour	10003472
Bipolar I disorder	10004939
Blunted affect	10005885
Bradyphrenia	10050012
Brief psychotic disorder with marked stressors	10048549
Brief psychotic disorder without marked stressors	10056395
Brief psychotic disorder, with postpartum onset	10006362
Catatonia	10007776
Charles Bonnet syndrome	10063354
Childhood psychosis	10061040
Clang associations	10009232
Constricted affect	10010778
Cotard's syndrome	10059591
Delusion	10012239
Delusion of grandeur	10012241
Delusion of reference	10012244
Delusion of replacement	10012245
Delusional disorder, erotomanic type	10012249
Delusional disorder, grandiose type	10012250
Delusional disorder, jealous type	10012251
Delusional disorder, mixed type	10012252
Delusional disorder, persecutory type	10053195
Delusional disorder, somatic type	10012254
Delusional disorder, unspecified type	10012255
Delusional perception	10012258

Dementia of the Alzheimer's type, with delusions	10012295
Depressive delusion	10063033
Derailment	10012411
Disorganised speech	10076227
Dyslogia	10054940
Echolalia	10014127
Echopraxia	10014128
Emotional poverty	10014557
Epileptic psychosis	10059232
Erotomanic delusion	10015134
Flat affect	10016759
Flight of ideas	10016777
Grandiosity	10018671
Hallucination	10019063
Hallucination, auditory	10019070
Hallucination, gustatory	10019071
Hallucination, olfactory	10019072
Hallucination, synaesthetic	10062824
Hallucination, tactile	10019074
Hallucination, visual	10019075
Hallucinations, mixed	10019079
Hypnagogic hallucination	10020927
Hypnopompic hallucination	10020928
Hypomania	10021030
Hysterical psychosis	10062645
Ideas of reference	10021212
Idioglossia	10068366
Illogical thinking	10021402
Illusion	10021403
Impaired reasoning	10071176
Inappropriate affect	10021588
Incoherent	10021630
Intrusive thoughts	10077275
Jealous delusion	10023164
Lack of spontaneous speech	10023615
Logorrhoea	10024796
Loose associations	10024825
Magical thinking	10025429
Major depression	10057840
Mania	10026749
Mixed delusion	10076429
Mutism	10028403
Neologism	10028916
Neuroleptic-induced deficit syndrome	10075295
Obsessive rumination	10056264
Paralogism	10077175
Paranoia	10033864
Paranoid personality disorder	10033869
Parkinson's disease psychosis	10074835
Paroxysmal perceptual alteration	10063117
Persecutory delusion	10034702
Perseveration	10034703
Postictal psychosis	10070669
Post-injection delirium sedation syndrome	10072851
Posturing	10036437
Poverty of speech	10036467
Poverty of thought content	10036468
Presenile dementia	10036631
Pressure of speech	10036649
Psychosis postoperative	10065617
Psychotic behaviour	10037249
Psychotic disorder	10061920
Psychotic disorder due to a general medical condition	10061921
Reactive psychosis	10053632
Rebound psychosis	10074833
Schizoaffective disorder	10039621

Schizoaffective disorder bipolar type	10068889
Schizoaffective disorder depressive type	10068890
Schizophrenia	10039626
Schizophreniform disorder	10039647
Schizotypal personality disorder	10039651
Senile dementia	10039966
Senile psychosis	10039987
Shared psychotic disorder	10040535
Social avoidant behaviour	10041243
Somatic delusion	10041317
Somatic hallucination	10062684
Speech disorder	10041466
Substance-induced psychotic disorder	10072388
Suspiciousness	10042635
Tachyphrenia	10064805
Tangentiality	10043114
Thinking abnormal	10043431
Thought blocking	10043495
Thought broadcasting	10052214
Thought insertion	10043496
Thought withdrawal	10043497
Transient psychosis	10056326
Vascular dementia	10057678
Verbigeration	10047313
Waxy flexibility	10047853
Additional Terms	
Formication	10017062
Substance-induced mood disorder	10072387

#### 4. Cardiac arrhythmias

SMQ 2000049: Cardiac arrhythmias	
PT	Code
Accelerated idioventricular rhythm	10049003
Accessory cardiac pathway	10067618
Adams-Stokes syndrome	10001115
Agonal rhythm	10054015
Anomalous atrioventricular excitation	10002611
Arrhythmia	10003119
Arrhythmia neonatal	10003124
Arrhythmia supraventricular	10003130
Arrhythmogenic right ventricular dysplasia	10058093
Atrial conduction time prolongation	10064191
Atrial fibrillation	10003658
Atrial flutter	10003662
Atrial parasystole	10071666
Atrial tachycardia	10003668
Atrioventricular block	10003671
Atrioventricular block complete	10003673
Atrioventricular block first degree	10003674
Atrioventricular block second degree	10003677
Atrioventricular conduction time shortened	10068180
Atrioventricular dissociation	10069571
Atrioventricular node dispersion	10077893
Baseline foetal heart rate variability disorder	10074638
Bezold-Jarisch reflex	10076999
Bifascicular block	10057393
Bradycardia	10006093
Bradycardia foetal	10006094
Bradycardia neonatal	10056471
Brugada syndrome	10059027
Bundle branch block	10006578
Bundle branch block bilateral	10006579
Bundle branch block left	10006580
Bundle branch block right	10006582

Cardiac arrest	10007515
Cardiac arrest neonatal	10007516
Cardiac death	10049993
Cardiac fibrillation	10061592
Cardiac flutter	10052840
Cardiac telemetry abnormal	10053450
Cardio-respiratory arrest	10007617
Cardio-respiratory arrest neonatal	10007618
Chronotropic incompetence	10068627
Conduction disorder	10010276
Defect conduction intraventricular	10012118
ECG P wave inverted	10057526
Electrocardiogram abnormal	10014363
Electrocardiogram ambulatory abnormal	10014369
Electrocardiogram change	10061116
Electrocardiogram delta waves abnormal	10014372
Electrocardiogram P wave abnormal	10050384
Electrocardiogram PQ interval prolonged	10053656
Electrocardiogram PQ interval shortened	10075328
Electrocardiogram PR prolongation	10053657
Electrocardiogram PR shortened	10014374
Electrocardiogram QRS complex prolonged	10014380
Electrocardiogram QT prolonged	10014387
Electrocardiogram repolarisation abnormality	10052464
Electrocardiogram RR interval prolonged	10067652
Electrocardiogram U-wave abnormality	10055032
Extrasystoles	10015856
Foetal arrhythmia	10016847
Foetal heart rate acceleration abnormality	10074642
Foetal heart rate deceleration abnormality	10074636
Foetal heart rate disorder	10061158
Foetal tachyarrhythmia	10077575
Heart alternation	10058155
Heart block congenital	10019263
Heart rate abnormal	10019300
Heart rate decreased	10019301
Heart rate increased	10019303
Heart rate irregular	10019304
Junctional ectopic tachycardia	10074640
Lenegre's disease	10071710
Long QT syndrome	10024803
Long QT syndrome congenital	10057926
Loss of consciousness	10024855
Lown-Ganong-Levine syndrome	10024984
Neonatal tachycardia	10049775
Nodal arrhythmia	10029458
Nodal rhythm	10029470
Nonreassuring foetal heart rate pattern	10074641
Pacemaker generated arrhythmia	10053486
Pacemaker syndrome	10051994
Palpitations	10033557
Parasystole	10033929
Paroxysmal arrhythmia	10050106
Paroxysmal atrioventricular block	10077503
Pulseless electrical activity	10058151
Rebound tachycardia	10067207
Reperfusion arrhythmia	10058156
Retrograde p-waves	10071187
Rhythm idioventricular	10039111
Sinoatrial block	10040736
Sinus arrest	10040738
Sinus arrhythmia	10040739
Sinus bradycardia	10040741
Sinus node dysfunction	10075889
Sinus tachycardia	10040752
Sudden cardiac death	10049418

Sudden death	10042434
Supraventricular extrasystoles	10042602
Supraventricular tachyarrhythmia	10065342
Supraventricular tachycardia	10042604
Syncope	10042772
Tachyarrhythmia	10049447
Tachycardia	10043071
Tachycardia foetal	10043074
Tachycardia paroxysmal	10043079
Torsade de pointes	10044066
Trifascicular block	10044644
Ventricular arrhythmia	10047281
Ventricular asystole	10047284
Ventricular dyssynchrony	10071186
Ventricular extrasystoles	10047289
Ventricular fibrillation	10047290
Ventricular flutter	10047294
Ventricular parasystole	10058184
Ventricular pre-excitation	10049761
Ventricular tachyarrhythmia	10065341
Ventricular tachycardia	10047302
Wandering pacemaker	10047818
Withdrawal arrhythmia	10047997
Wolff-Parkinson-White syndrome	10048015
Wolff-Parkinson-White syndrome congenital	10049291

5. Combined insomnia

PT	Code
Insomnia	10022437
Initial insomnia	10022035
Middle insomnia	10027590
Terminal insomnia	10068932

6. Weight decreased

PT	Code
Weight decreased	10047895

7. Decreased appetite

PT	Code
Decreased appetite	10061428

8. Psychosis/Mania (subgroup of neuropsychiatric events)

PT	Code
Catatonia	10007776
Delusion	10012239
Somatic delusion	10041317
Delusional perception	10012258
Formication	10017062
Hallucination	10019063
Hallucination, auditory	10019070
Hallucination, gustatory	10019071
Hallucination, olfactory	10019072
Hallucination, tactile	10019074
Hallucination, visual	10019075
Hallucinations, mixed	10019079
Hypnagogic hallucination	10020927
Hypnopompic hallucination	10020928
Illusion	10021403
Paranoia	10033864
Psychotic disorder	10061920
Substance-induced psychotic disorder	10072388
Thinking abnormal	10043431
Hypomania	10021030
Mania	10026749

Substance-induced mood disorder	10072387
---------------------------------	----------
